- (a) Screening and Baseline Visits may be combined as determined appropriate per the investigator. Any procedure that is to be performed at both visits should only be conducted once for a combined visit.
- (b) UDS to be done at Screening and Baseline. UDS kits will be supplied by the sponsor for the testing at the clinic. UDS results must be negative. This includes benzodiazepines and opiates for which there is no prescription (including oxycodone) at Screening and Baseline. Results must be confirmed prior to conducting the Baseline Visit.
- (c) Height at Screening only; weight at Screening, Baseline, and Week 12.
- (d) Subjects who signed an informed consent for PGx testing will have blood samples for PGx analysis and these will be collected as follows: 2×3 mL for DNA on Day 1; 2×2.5 mL for RNA predose on Day 1 and at Week 12 (Visit 6).
- (e) To be collected at Screening or combined Screening/Baseline Visit.
- (f) Urine hCG pregnancy tests will be performed at Screening and Baseline and for all other visits during the Treatment Period for women of childbearing potential only. Serum hCG pregnancy tests will be performed at Baseline and End of Study/Early Termination visits for all females. For combined Screening and Baseline Visits, there will be 1 urine and 1 serum hCG. Subjects may be enrolled with a negative urine hCG; however if the serum hCG is positive the subject must be withdrawn from study drug immediately and withdrawn from the study as soon as possible.
- (g) Subject who are women of childbearing potential will be provided with information on acceptable methods of contraception as part of the subject informed consent process and will be asked to sign a consent form stating that they understand the requirements of pregnancy and donation of ova during the course of the study and for 30 days after the last dose of study drug.
- (h) Dose adjustments should occur during regularly scheduled visits, or subjects should return for an Unscheduled Visit.

Rationale for Amendment

Documentation of antidepressant change, and satisfaction with change in treatment was noted in Section 9.3, but was not listed in the table of procedures in error. Clinician and subjects satisfaction with GAS is being added to assess the GAS approach in clinical practice and to guide future GAS work. Footnote e was added and subsequent footnotes were renumbered. Footnote g was edited to match inclusion criteria and section 9.1.10.

3.0 LIST OF ABBREVIATIONS

5-HT	Serotonin
AE	adverse event
ALT	alanine aminotransferase
AST	aspartate aminotransferase
CGI-I	Clinical Global Impression Scale-Improvement
CGI-S	Clinical Global Impression Scale Severity
CRO	contract research organization
C-SSRS	Columbia Suicide Severity Rating Scale
DRESS	drug reaction with eosinophilia and systemic symptoms
DSM-5	Diagnostic and Statistical Manual of Mental Disorders, Fifth Edition
Comp	Company Confidential Information
any	
ECG	Electrocardiogram
Confid	
ecr	electronic case report form
Inform	
FAS	full analysis set
ation	
FSH	follicle-stimulating hormone
GAS	Goal Attainment Scale
GCP	Good Clinical Practice
hCG	human chorionic gonadotropin
ICH	International Conference on Harmonisation
ID	Identification
IEC	independent ethics committee
INR	international normalized ratio
IRB	institutional review board
IxRT	Interactive Response Technology
Compan	Company Confidential Information
Y	
LFT	liver function tests
Confide	
MDD	major depressive disorder
Ma	
Informat	
MDE	major depressive episode
ion	
MedDRA	Medical Dictionary for Regulatory Activities
PGx	Pharmacogenomics
PDQ-D	Perceived Deficits Questionnaire-Depression
PHQ-9	Patient Health Questionnaire
PPS	per protocol set
PTE	pretreatment event
Q-LES-Q	Quality of Life and Enjoyment and Satisfaction Questionnaire
QD	once daily
Compan	Company Confidential Information
Y	
SAE	serious adverse event
Confide	
SJS	Stevens-Johnson syndrome
ma	
Informati	
SUSAR	suspected unexpected serious adverse reaction
on	

CONFIDENTIAL

TEN	toxic epidermal necrolysis
UDS	urine drug screen
ULN	upper limit of normal
Company Confidential Information	
WHO	World Health Organization
WHO-5	5-item World Health Organization Well-Being Index
n	

4.0 OBJECTIVES

4.1 Primary Objective

To determine the effectiveness of treatment with vortioxetine on subject goal achievement after a change in antidepressant medication for the treatment of major depressive disorder (MDD).

4.2 Secondary Objectives

To determine the effectiveness of treatment with vortioxetine on depressive symptoms/outcomes, clinical global impression, cognitive impairment, and quality of life in subjects with MDD.

4.3 Additional Objectives

- To determine the effectiveness of treatment with vortioxetine on cognitive performance and functionality in subjects with MDD.
- To determine the effectiveness of treatment with vortioxetine on work performance in subjects with MDD.
- To determine the effectiveness of treatment with vortioxetine on general health status and well-being in subjects with MDD.
- To assess health care utilization and the safety and tolerability of vortioxetine in subjects with MDD.

4.4 Study Design

This study is an open-label, single-arm, multicenter, prospective, phase 4, interventional, flexible dose study (as per the Trintellix US package insert) to determine the effectiveness of treatment with vortioxetine on subject goal achievement after a change in antidepressant medication for the treatment of MDD.

This study is comprised of a 3-week Screening Period (maximum 21 days), to be followed by a 12-week Treatment Period and a 4-week Safety Follow-up Period. Study visits will occur at Baseline (Day 1), and Weeks 2, 4 (Telephone), 6, 9 (Telephone), and 12. This study will enroll approximately 120 subjects and will be conducted at approximately 25 sites in the United States.

This study will enroll men and women between the ages of 18 and 65, inclusive, with a primary diagnosis of MDD, who have previously been treated within 6 weeks of Screening or are currently being treated for a major depressive episode (MDE) with an approved antidepressant for 6 weeks or longer at an adequate dose. Subjects who are dissatisfied with their current or recent antidepressant and are interested in a change in antidepressant treatment will be eligible for Screening.

The change in antidepressant medication will be based on the investigator's judgment in collaboration with the subject's level of dissatisfaction with their current or recent antidepressant treatment (ie, residual mood symptoms, intolerable side effects). Subjects also need to be eligible

per the Trintellix US package insert and sign and date a written, informed consent form and any required privacy authorization prior to the initiation of any study procedures.

The investigator or the investigator's designee will access the Interactive Response Technology (IxRT) at Screening to obtain the subject study number. At the Baseline Visit, if the subject has satisfied all of the inclusion criteria and none of the exclusion criteria for enrollment, the subject will be enrolled using the IxRT. Subjects will be instructed on when to take the first dose of study drug. The dosing (both initial and adjustments) will be determined by investigator or designee as per routine clinical practice and per approved Trintellix labeling. Subjects will determine treatment goals with their clinicians using the Goal Attainment Scale (GAS) adapted for an MDD population. The subject and clinician will work to establish 3 goals at Baseline. One goal will be determined based on the subject's self-defined objectives. Two goals will be selected from the following predefined categories representing MDD residual symptoms, antidepressant side effects, and common reasons for a change in antidepressant medication, including but not limited to:

MDD Domains	Psychological	Motivation	Emotional	Physical/ Functional	Cognition
Predefined goal categories:	-Depressed mood -Anxious mood	-Lack of motivation	-Low self esteem -Anhedonia	-Fatigue -Insomnia -Muscle tension -Sexual dysfunction -Weight gain	-Problems concentrating -Short term memory problems -Difficulty staying focused -Difficulty paying attention -Problems thinking clearly

[figure not shown]
A prepopulated list of categories will be provided in the structured guidance for goal assessment, including behavioral examples describing goals and observable benchmarks to help clinicians set the appropriate goals with subjects. Goals will be set at Baseline/Visit 1. Progress will be evaluated at the Week 6 visit. At the Final Visit the goals will be assessed based on levels of achievement on a 5-point scale. Investigators will be trained on goal setting/goal assessment and monitored for ability in key domains of goal setting (eg, attainability of goals, use of observable objectives and benchmarks, equidistance of scaling, general level of difficulty, goal differentiation, and overall quality).

A safety follow-up phone call will be made 4 weeks after completion of the 12 weeks of treatment. Subjects who discontinue or who are withdrawn prior to study completion will come to the site for an Early Termination Visit as soon as possible and will be contacted for a safety follow-up 4 weeks after the last dose of study medication.

Enrollment caps may be implemented throughout the course of the study based on the patient reported outcome (ie, Patient Health Questionnaire (PHQ-9) and Perceived Deficits Questionnaire-Depression (PDQ-D)) scores at Baseline.

A futility analysis will be performed at an interim analysis with approximately 60 subjects completing Week 12. If the futility analysis indicates that the study should be discontinued, the final analyses will be conducted for all enrolled subjects. Details for the futility analyses are in the Interim Analysis section of this SAP.

Figure 4.a Schematic of Study Design

(a) Recommended starting dosage is 10 mg/day as ideal dosage. Dosage may be decreased to 5 mg/day at discretion of the investigator or designee.

[figure not shown]
(b) If all screening activities are completed and the subject meets the eligibility criteria the Screening and Baseline Visits can be combined into 1 visit.

(c) Subjects currently on an antidepressant at Screening will be discontinued in a manner that is consistent with labeling recommendations and conventional medical practice prior to Baseline.

5.0 ANALYSIS ENDPOINTS

The GAS, adapted for MDD is being used as primary endpoint in this study. As this is an adaptation of an existing instrument the results will provide novel outcome data for the goal attainment literature. Therefore, secondary endpoint assessments with validated instruments will provide additional confirmation of the effectiveness of vortioxetine in treating MDD when current antidepressant treatment is not adequate.

The following outcome measures will be used for secondary and exploratory endpoints as they are frequently used to assess clinical response: PHQ-9, PDQ-D, Quality of Life and Enjoyment and Satisfaction Questionnaire (Q-LES-Q), 5-item World Health Organization Well-Being Index (WHO-5), Clinical Global Impression-Severity (CGI-S), Clinical Global Impression-Improvement (CGI-I), Company Confidential Information

Measures have been taken regarding the methodology of this study to assess suicidal risk. The selection criteria exclude the participation of subjects at significant risk for suicide. Throughout the study, signs of suicidal risk will be assessed both by rating scale assessment (C-SSRS) and by investigators' clinical judgment. Subjects will be withdrawn from the study in case of such risk. Furthermore, subjects will be screened for the history of suicidal behavior.

5.1 Primary Endpoint

The primary endpoint is to estimate the proportion of subjects who achieve their identified goals as demonstrated by an outcome Goal Attainment Scale (GAS) Score of ≥ 50 at Week 12.

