5.2 Endpoints

5.2.1 Primary Endpoint

The primary endpoint is to estimate the proportion of subjects who achieve their identified goals as demonstrated by an outcome Goal Attainment Scale (GAS) Score of \geq 50 at Week 12.

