7.8.1 Primary Efficacy Endpoint

The GAS is a tool to measure the progress each subject has towards achieving their individualized goals. While the outcome measure is unique to each subject, standardized scoring is applied to allow for statistical analysis.

The GAS allows for 1 of 2 types of goals to be set:

- (1) Subject defined goals allow a “subject’s chief complaint” approach taken towards establishing the goal, with no specific limitations set for the type or focus of the goal, beyond requiring that it meets the basic standards of measurability, equidistance, and difficulty.
- (2) Domain-defined goals are more structured in nature, presenting the subject with an array of broadly defined domains and more specific subdomains. After selecting an appropriate domain and (where applicable) subdomain, the clinician will work with the subject to establish a specific goal that fits within the selected category.

For GAS, a total of 3 goals will be selected, 1 subject defined and 2 from pre-defined domain categories. A 5-point rating scale will then be applied to each of the 3 goals. A semi-structured interview will be conducted with each subject to conduct goal-setting at the outset of the study.

Another evaluation will take place at Week 6 and Week 12/End of Study visits or at Early Termination Visit (as applicable) to determine the level of progress at that time, with assignment of appropriate scores. It takes subjects approximately 45 minutes to complete the GAS.

Calculating the Overall GAS

The goals identified are incorporated into the single GAS score by applying a formula:

$$\text{Overall GAS} = 50 + \frac{10 * \sum(w_i x_i)}{\sqrt{(1-\rho) \sum w_i^2 + \rho(\sum w_i)^2}}$$

Where:

w_i = the weight assigned to the i th goal (if equal weights, $w_i = 1$)

x_i = the numerical value achieved (between -2 and +2)

ρ = the expected correlation of the goal scales

(For practical purposes, most commonly approximates to $\rho=0.3$)

For this study, a choice of weight is based on importance of the goal. Weight is 1, 2, and 3 for least important, moderately important and most important goals, respectively. The expected correlation of 0.3 was selected for this study.

The GAS will be summarized for both Week 6 and Week 12 using both percents of response and as a continuous score. An overall GAS score greater than 50 is considered as a response.

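### The primary result is labelled as subjects achieving their goals, but the GAS cut-off is a compensatory weighted sum that a subject can pass with a goal rated below 0

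*SAP*

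**What the plan says.** Protocol 5.2.1 states: "The primary endpoint is to estimate the proportion of subjects who achieve their identified goals". SAP 5.1 uses the same description, "the proportion of subjects who achieve their identified goals", and gives the criterion as a "Goal Attainment Scale (GAS) Score of ≥ 50 at Week 12". Protocol 13.1.3 and SAP 7.8 repeat it.

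SAP 7.8.1 gives the scoring:

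- Goals: "For GAS, a total of 3 goals will be selected, 1 subject defined and 2 from pre-defined domain categories".
- Each goal is rated on five levels, from -2 to +2.
- Weights: "Weight is 1, 2, and 3 for least important, moderately important and most important goals, respectively".
- Correlation constant: "The expected correlation of 0.3 was selected for this study".
- Response rule: "An overall GAS score greater than 50 is considered as a response". This is a strict inequality, whereas the endpoint sections, the sample size section (SAP 6.0) and the interim section (SAP 7.10) use ≥50.

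The same section summarises GAS at Weeks 6 and 12 as response percentages and as a continuous score. The visible text sets no minimum for any single goal. It plans no count of goals attained and does not say what each of the five levels means.

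**The concern.** The description speaks of goals in the plural, and each subject has three. The rule that is meant to demonstrate their achievement looks only at a weighted total. A subject can therefore be counted as having achieved the identified goals while one of them, or occasionally two, is rated below 0.

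This matters more here than in a controlled trial. The study has one arm and no formal test of the primary endpoint, so the responder proportion and its interval are the primary result. Protocol 6.2.3 calls the instrument an adaptation that will yield novel data, so readers cannot be assumed to know how this version should be read. If the proportion is taken as the share of subjects who met their goals, it can say more than the data show.

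**Working it through.** **1. The plan's own figure.** Inputs from SAP 6.0: p = 0.50, n = 100, 95% CI. Half-width = 1.96 × √(0.5 × 0.5 / 100) = 0.098. This matches the stated ±0.098.

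**2. What the cut-off means.** With weights 1, 2, 3 and ρ = 0.3 (SAP 7.8.1), Σw² = 14 and (Σw)² = 36. The denominator is √(0.7 × 14 + 0.3 × 36) = √20.6 = 4.539. So

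GAS = 50 + 10 × (x₁ + 2x₂ + 3x₃) / 4.539,

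where x₃ is the most important goal. GAS ≥ 50 is the same as x₁ + 2x₂ + 3x₃ ≥ 0. The constant ρ rescales the score but does not change who responds.

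An ordinary case that responds under either inequality is (-1, 0, +1): the sum is -1 + 0 + 3 = 2 and GAS = 50 + 20/4.539 = 54.4. With two goals below 0, (-1, -1, +2) gives a sum of 3 and GAS = 56.6.

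**3. All 5³ = 125 rating patterns**, with a goal counted as missed if x < 0:

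| | GAS ≥ 50 | GAS > 50 |
|---|---|---|
| Responder patterns | 67 | 58 |
| All three goals at 0 or better | 27 | 26 |
| One goal missed | 34 | 29 |
| Two goals missed | 6 | 3 |
| At least one missed | 40 | 32 |
| Most important goal missed | 7 | 4 |

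The last row overlaps the rows above it. No pattern with all three goals missed is a responder. Nine patterns score exactly 50 and change status between the two columns. One of them is (0, 0, 0), which is a non-responder under >50.

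**4. From patterns to subjects.** The documents give no rating distribution, so one must be assumed: latent normal ratings with SD 1, rounded to -2 to +2, a common mean, a common correlation, and 2 million simulated subjects.

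| Mean | Correlation | GAS ≥ 50 | GAS > 50 | All three ≥ 0 | Responders (≥50) missing at least one | Missing two |
|---|---|---|---|---|---|---|
| 0 | 0 | 55.3% | 44.8% | 33.1% | 40.1% | 4.4% |
| 0 | 0.3 | 54.6% | 45.4% | 40.7% | 25.5% | 2.5% |
| 0 | 0.6 | 55.0% | 45.1% | 48.7% | 11.4% | 1.0% |
| +0.5 | 0 | 81.6% | 73.8% | 59.6% | 27.0% | 1.6% |
| +0.5 | 0.3 | 77.6% | 70.1% | 64.3% | 17.1% | 1.1% |
| +0.5 | 0.6 | 75.5% | 67.2% | 69.7% | 7.6% | 0.5% |

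Under ≥50, every subject with all three goals at 0 or better is a responder, so the missing share is one minus the ratio of the two rates. In the central case this is 1 - 0.407/0.546 = 25.5%. The gap between the two rates there is 54.6 - 40.7 = 13.9 points, against a planned half-width of 9.8 points. At mean 0 it is 22.2 points at correlation 0 and 6.3 points at correlation 0.6.

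**5. The most important goal.** In the central case 3.7% of responders miss it. Over all subjects, the proportion with it at 0 or better is P(Z ≥ -0.5) = 69.1% at mean 0 and P(Z ≥ -1.0) = 84.1% at mean +0.5.

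**The case against.** **The rule is disclosed.** Each description of the endpoint is followed by its GAS criterion, and the formula, weights and constant are printed. This stands: the issue is the label, not a hidden rule or a wrong calculation.

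**Nothing requires all three goals to be met.** A reader might infer that only a subject with every goal at 0 or better is a true responder and that the composite miscounts the rest. The documents do not say this; no text asks for all the goals. The all-three proportion is a supportive description, not the correct primary endpoint.

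**Compensation is what importance weighting is for.** This also stands. In the central case 12.0 of the 25.5 percentage points are responders who missed only the lowest-weighted goal.

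**Extreme cases are not typical.** A reader might take (-2, -2, +2), with two goals at the lowest level, as representative. It scores exactly 50, so it is a non-responder under the strict wording of SAP 7.8.1. In the central model it is about 0.01% of responders.

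**Pattern counts are not subject shares.** A reader might infer from 40 of 67 that 60% of responders miss a goal. That would require all 125 patterns to be equally likely. The model shares are lower and depend on assumptions; the ρ of 0.3 is a scoring constant, not an observed correlation.

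**The missing table may exist elsewhere.** Additional endpoints are redacted, and SAP 7.8.4 refers GAS evaluation to a separate validation plan. Part of the remedy may already be planned there.

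**Conclusion.** The point holds as one of labelling and supportive reporting. The cut-off identifies subjects whose weighted attainment is at or above the score's centre; it does not show that each identified goal was achieved. That follows exactly from the formula and holds under either inequality.

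The size for subjects rests on the assumed model. With means from 0 to +0.5 and correlations from 0 to 0.6, about 8% to 40% of ≥50 responders have at least one goal below 0 (about 26% in the central case), and about 0.5% to 4% have two. Calling such a goal missed rests on reading 0 as the expected level, inferred from a score centred at 50.

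A reader might also infer that the headline rate always exceeds the all-three rate. That is true under ≥50. Under >50 it need not be: at mean 0 and correlation 0.6 the rates are 45.1% and 48.7%, because (0, 0, 0) is then excluded. The inequality therefore has to be settled before the two figures are set side by side.

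**What to change.** - Keep the primary calculation.
- Reconcile ≥50 with >50, so that SAP 7.8.1 agrees with the endpoint, sample size and interim sections.
- Describe the result as *overall weighted goal attainment (GAS at or above 50)* in the protocol, SAP and report, and state the meaning of each of the five rating levels.
- Beside the primary rate, report with 95% CIs the proportion with all three goals at 0 or better and the proportion with the most important goal at 0 or better.

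The ratings are already needed to compute the score, so the cost is a wording change and one table, with no new data and no change in sample size. At p = 0.407 and n = 100 the half-width would be 1.96 × √(0.407 × 0.593 / 100) = 0.096, close to the planned precision. The downside for the sponsor is that, under ≥50, the all-three figure cannot exceed the primary rate and will usually be lower. The most-important-goal figure was higher than the primary rate in every modelled case. If the redacted sections or the validation plan already contain these summaries, a cross-reference is enough.

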5.2 Secondary Endpoints

The secondary endpoints are:

- Mean change from Baseline in total GAS Score at Week 6 and Week 12.
- Change from Baseline in depression severity as measured by the Patient Health Questionnaire (PHQ-9) Score at Week 6 and 12.
- Change from Baseline in perceived cognitive deficits and cognitive function as measured by the Perceived Deficits Questionnaire-Depression (PDQ-D) at Week 6 and 12.
- Change from Baseline in Quality of Life Enjoyment and Satisfaction Scale (Q-LES-Q) Score at Week 12.
- Change from Baseline in 5-item World Health Organization Well-Being Index (WHO-5) Score at Week 12.
- Change from Baseline in Clinical Global Impression Scale Severity (CGI-S) at Week 12.
- Clinical Global Impression Scale-Improvement (CGI-I) Score at Week 12.

5.3 Additional Endpoints

The exploratory/additional endpoints include:

Company Confidential Information

5.4 Safety Assessments

Safety and tolerability of vortioxetine will also be evaluated using the following general assessments:

- Adverse events (AEs).
- AEs leading to discontinuation.
- Weight.
- Columbia-Suicide Severity Rating Scale (C-SSRS).

